### 2.3 STUDY AIMS/HYPOTHESES

This study will provide a comprehensive investigation of the causal role and functional interactions between theta and alpha oscillations in the selection and suppression of information processing in the human brain. This will allow us to assess whether these oscillations support dependent cognitive processes, and if this dependence is fundamental in coordinating information processing in the brain.

We hypothesize that theta oscillations in frontal cortex play a causal role in the prioritization of working memory representations and alpha oscillations in parietal cortex play a causal role in the suppression of working memory representations. Furthermore, in-phase theta oscillations, but not alpha oscillations, are critical for synchronizing activity between frontal and parietal cortex. To investigate this model, we propose two phases to the experiment and aims that are defined as either a “primary outcome” or “secondary outcome.” Note that for each of these aims has a corresponding statistical analysis described in section 11.

*Phase One* overarching goal: Investigate the causal role of frontal theta and parietal alpha oscillations in the prioritization and suppression of working memory representations.

Aim 1 (primary outcome): Stimulation that is aligned to the endogenous activity of the brain (frontal theta and parietal alpha) is hypothesized to improve performance whereas the mismatched frequency of stimulation is hypothesized to decrease performance (frontal alpha and parietal theta). Performance is assessed using Pashler’s working memory capacity metric.

Aim 2 (primary outcome): Stimulation is hypothesized to increase the targeted frequency of stimulation relative to arrhythmic stimulation. This aim will provide evidence of target engagement, i.e. that stimulation is effective at modulating the targeted rhythm.

Aim 3 (secondary outcome): Theta and alpha oscillations are hypothesized to play antagonistic roles

CONFIDENTIAL

whereby theta oscillations are associated with an increase in neural excitability and alpha oscillations are associated with a decrease in neural excitability. Therefore, we will investigate the impact of stimulation on other frequency band. Theta stimulation is hypothesized to decrease the amplitude of alpha oscillations and alpha stimulation is hypothesized to decrease theta oscillations.

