#### 4 BASIC STUDY DESIGN

This study is a pilot, five-session study with transcranial magnetic stimulation (TMS), electroencephalography (EEG), and magnetic resonance imaging (MRI) to understand the neural oscillatory basis of output-gating. The first session of the experiment will be screening session, in which participants provide written consent to participate, screened for colorblindness, complete questionnaires, and perform a working memory task with retrospective cues. Participants will be invited back to the second session if they show a benefit to their working memory percent correct by use of the informative retro-cue relative to the uninformative neutral cue. This session will also be used to select the number of items that will be used in the working memory task for subsequent sessions. The criteria for difficulty titration is task performance between 60% and 85% correct for retro-cue trials and a benefit of at least 5% greater than neutral cue trials. Thus, different participants will perform the task with different numbers of items to be encoded into working memory. Titration of task difficulty as described here is critical for experiments that use causal manipulation (e.g. transcranial magnetic stimulation) to modulate performance. If participants are performing at ceiling (close to 100%) or at floor (close to random chance), then any experimental manipulation of behavior is less likely to impact performance as the task is too "easy" or too "hard." For the second session of the experiment,

[figure not shown]

Fig1. Experimental design consists of five sessions. The two phases of the experiment randomize and counterbalanced different parameters of stimulation for the 4th and 5th session. w/ = with. WM = working memory.

participants perform the working memory retro-cue task while EEG is recorded. In addition, participants will complete a simple perception color task in which participants see a color and choose the matching color from the color circle. This task tests for the precision of perception throughout the color circle. The EEG data from the second session will be preprocessed and a Morlet wavelet convolution analysis will be conducted. The resulting spectrogram will be contrasted between the informative retro-cue and uninformative neutral cue to derive the theta frequency with peak amplitude in

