#### 6.5.2 RETRO-CUE WORKING MEMORY TASK

The retro-cue working memory task consists of five epochs. In the first epoch, the participant is presented with lateralized stimuli, colored squares, in both the left and right visual hemifield. The participant is given one second to encode these items into memory. During the screening participants will be presented with one, two, or three colored squares in both visual fields, and in subsequent session there is a fixed number of stimuli. In the second epoch, there is a one second delay period over which the iconic memory of the colored squares decays. In the third epoch, the participant is presented with an informative retro-cue, an arrow to the left or right, that is 100% predictive of the upcoming probe, or an uninformative neural cue, an arrow pointing in both directions. In the fourth epoch, participants must maintain the items in memory over a two second delay. It is during this epoch, after the presentation of the retro-cue that TMS is delivered in sessions four and five. Finally, in the probe epoch participants are presented with a dotted outline of the squares on the left or the right and solid lines around the item to be recalled. At the center of the screen is a color wheel and a blank square. Participants move a joystick towards the direction of the color in the color wheel that they wish to select. The square in the center changes color to match the selected color by the participant. Once the color is selected, the participant pulls the trigger on the joystick with their index finger. Participants are instructed to be both fast and accurate.

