### 11.1 STATISTICAL ANALYSIS STRATEGIES

The statistical analysis plan below aligns with the aims that are described in Section 2.3. all statistical estimates of population parameters will be tabulated along with corresponding confidence intervals (CIs) to convey levels of precision / imprecision. All hypothesis tests that yield large p-values ( $p>0.05$ ) will be reported as being inconclusive.

*Phase One* overarching goal: Investigate the causal role of frontal theta and parietal alpha oscillations in the prioritization and suppression of working memory representations. To control for non-specific effects of rhythmic TMS, we will use an active control: arrhythmic TMS (randomized inter-pulse-interval) that is matched to the target stimulation in number of pulses and temporal duration. All analyses will be performed on the difference from condition-matched arrhythmic TMS. The key analyses are built upon a three-way parallel arms design: with factors TMS frequency (theta versus alpha), location (frontal versus parietal), and cue direction (left versus right retro-cue). There is an equal number of trials for each of these conditions and there are 75 trials for each condition per participant.

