Aim 1 (primary outcome): Stimulation that is aligned to the endogenous activity of the brain (frontal theta and parietal alpha) is hypothesized to improve performance whereas the mismatched frequency of stimulation is hypothesized to decrease performance (frontal alpha and parietal theta). Performance is assessed using Pashler's working memory capacity metric ( $k$ ) which is defined as:  $k = N * \frac{HR*FA}{1-FA}$  where  $N$  is the number of the items that are held in memory. HR is the hit rate defined as the percent correct for trials where the probe does not match the encoding array. FA is the false alarm rate defined as the percent incorrect for trials where the probe does match the encoding array. We will perform a two-way repeated-measures ANOVA with two within-participant factors TMS site (frontal or parietal) and TMS frequency (theta or alpha). We expect to observe a small p-value ( $p < 0.05$ ) for the interaction between TMS site and TMS frequency. Post-hoc t-tests will be performed using Tukey's method to control for multiple comparisons. *Sensitivity analysis*: In addition to calculating changes in working memory capacity, the impact on hit rate, false alarm rate, and overall accuracy will be calculated. The robustness of these effects will be estimated using an individual differences analyses where baseline performance is used as a covariate to improve model estimation. Finally, the titration of working memory load by participant will be added as a covariate to explore if this factor changes the model estimation. These are framed as exploratory analyses.

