forms of arrhythmic stimulation are used: arrhythmic-in-synchrony stimulation delivers simultaneous stimulation to the two sites, but there is no consistent frequency component to the stimulation. Thus, activity in the two sites may be synchronized but not in a frequency-specific manner. The second control condition for stimulation is arrhythmic-independent where two trains of TMS are delivered in random patterns. There is no synchronization between the two pulse trains. Arrhythmic-independent controls for frequency and synchrony specificity of stimulation. All analyses will be performed on the difference from condition-matched arrhythmic TMS (in-phase minus arrhythmic-in-synchrony and anti-phase minus arrhythmic-independent). The key analyses are built upon a three-way design: with factors TMS frequency (theta and alpha), TMS alignment (in-phase and anti-phase), and cue direction (left and right retro-cue).

**Aim 6 (primary outcome):** Stimulation that is delivered in-phase to frontal and parietal cortex in the theta frequency is hypothesized to increased working memory capacity relative to anti-phase theta stimulation. Working memory capacity is quantified using Pashler's metric (see Aim 1). We will perform a two-way repeated-measures ANOVA with a between participants factor of TMS frequency (theta and alpha) and within-participants factor of TMS alignment (in-phase and anti-phase). We hypothesize to find a significant interaction ( $p < 0.05$ ) between TMS frequency and TMS alignment such that in-phase TMS in theta-frequency increases working memory capacity. Post-hoc t-tests will be performed using Tukey's method to control for multiple comparisons. *Sensitivity analysis:* Similar to aim 1, the impact of stimulation on hit rate, false alarm rate, and overall accuracy will be calculated. The robustness of these effects will be estimated using an individual differences analyses where baseline performance is used as a covariate to improve model estimation. Finally, the titration of working memory load by participant will be added as a covariate to explore if this factor changes the model estimation. These are framed as exploratory analyses.

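### As printed, the capacity score for Aims 1 and 6 multiplies hit rate by false-alarm rate, so it rises with false alarms and gives a perfect participant zero

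*Combined protocol and SAP*

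**What the plan says.** Section 2.3 states for Aim 1 that "Performance is assessed using Pashler’s working memory capacity metric". Section 11.1, Aim 1, gives the only formula for that metric in the documents: k = N × (HR × FA)/(1 − FA), with N the number of items held in memory. It then defines the two rates: "HR is the hit rate defined as the percent correct for trials where the probe does not match the encoding array", and "FA is the false alarm rate defined as the percent incorrect for trials where the probe does match the encoding array". HR is therefore a measure of success and FA a measure of error.

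Aim 6, the primary behavioural outcome of phase two, takes its metric from Aim 1. Both aims read a higher k as better performance. Aim 1 expects improvement from frontal theta and parietal alpha stimulation, and Aim 6 expects an interaction "such that in-phase TMS in theta-frequency increases working memory capacity". For phase one, Section 11.1 adds: "All analyses will be performed on the difference from condition-matched arrhythmic TMS". Phase two uses the same kind of difference. The direction of change in k is therefore the result itself.

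Two further statements set the working range. Section 4: "The criteria for difficulty titration is task performance between 60% and 85% correct for retro-cue trials". Section 6.5.2: at screening, participants are "presented with one, two, or three colored squares in both visual fields", and the number is fixed afterwards.

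**The concern.** A capacity score should be highest for a participant who makes no errors and should fall as either kind of error becomes more common. The printed expression does neither. Its numerator is a success rate times an error rate, so it vanishes when false alarms vanish and grows as they grow.

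This expression defines the primary behavioural outcome of both phases. If it were applied as written, stimulation that reduced false alarms could show up as a loss of capacity, and the key interaction could be significant in the direction opposite to the real effect. No other section restates the formula, so nothing in the documents corrects it.

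**Working it through.** **The plan's own figure first.** Section 11.2 gives an effect size of 0.532, 95% power and 48 participants. Treated as a paired t-test, two-sided at 0.05 (sidedness is not stated), d = 0.532 with n = 48 gives power 0.9505. The sample size reproduces, and it does not use the formula for k.

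**Inputs.** The written formula and the HR and FA definitions come from Section 11.1, Aim 1. The 60% to 85% accuracy window comes from Section 4, and set sizes 1 to 3 from Section 6.5.2. I use N = 2 below; N only scales k, so it does not affect any sign.

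**Comparison form (an assumption about intent).** The documents give no alternative formula. Suppose k of N items are held and the remainder are guessed at rate FA. Then HR = k/N + (1 − k/N) × FA, and solving for k gives k = N × (HR − FA)/(1 − FA).

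**Slopes of the written form.**
- dk/dFA = N × HR/(1 − FA)², positive whenever HR > 0. More false alarms give a higher score.
- dk/dHR = N × FA/(1 − FA), also positive for FA > 0. Errors on non-match probes alone lower the score, as they should.
- With equal error rates (HR = 1 − FA), k = N × (1 − FA) × FA/(1 − FA) = N × FA. The score is then set size times error rate.

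**Values at N = 2.**

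| HR / FA | Written k | Difference form |
|---|---|---|
| 1.00 / 0.00 | 0 | 2.00 |
| 0.85 / 0.15 | 0.30 | 1.65 |
| 0.80 / 0.20 | 0.40 | 1.50 |
| 0.60 / 0.40 | 0.80 | 0.67 |
| 0.50 / 0.50 | 1.00 | 0 |

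If the two error rates are equal, rows 2 and 4 are the limits of the titration window. Across it, the written score rises as performance falls.

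**Three improvements from HR 0.80 / FA 0.20, N = 2.**

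| Change to | Written k | Difference form |
|---|---|---|
| 0.85 / 0.15 (both rates) | −0.100 | +0.147 |
| 0.80 / 0.15 (FA only) | −0.118 | +0.029 |
| 0.85 / 0.20 (HR only) | +0.025 | +0.125 |

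**When the sign flips.** Setting the total change to zero, written k starts to fall once the drop in FA exceeds FA × (1 − FA)/HR times the gain in HR. With HR = 1 − FA this multiple is FA itself: 0.15 at 0.85/0.15, 0.20 at 0.80/0.20 and 0.40 at 0.60/0.40. Equal gains on both rates (a multiple of 1) therefore reverse the sign throughout the window.

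**Illustrative simulation of the Aim 1 interaction.** Assumptions: 48 participants; N equally likely to be 1, 2 or 3; baseline accuracy uniform from 60% to 85%, with HR = accuracy and FA = 1 − accuracy; 75 match and 75 non-match trials per cell; binomial noise only. Frontal theta and parietal alpha improve and the mismatched cells worsen by the same amount, each minus its arrhythmic control.
- Both rates shifted by 1.5 to 2 points, site within participants: the written score is significant in the wrong direction in about 42% to 66% of runs.
- The same shifts with site between arms (24 per arm): about 25% to 38%.
- FA only, 2 points: wrong direction in about 91% (within) or 65% (between). The difference form has only about 24% power here in the within-participant case.
- HR only, 2 points, within: the written score is significant in the right direction in about 15%, against about 85% for the difference form.

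Under another set of assumptions (N = 2, mean HR 0.80 and FA 0.20, between-person SD 0.05, site within participants), a 2-point shift in both rates gives wrong-direction significance in 89%. The percentages move a good deal with the inputs; the algebra does not.

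**The case against.** **It may be a reading fault.** The point turns on one symbol in a formula extracted from PDF, with no second occurrence to compare. A minus sign could have been misread as a multiplication sign. The minus in the denominator survived, which makes this less likely but does not exclude it. If the printed page shows HR − FA, the point about the formula falls.

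**It may be a slip that the scoring code does not share.** The plan names an established metric and treats higher as better throughout. A reader might infer that the trial will score participants with the product, or that a harmful stimulation will be reported as beneficial. The documents show no code and support neither inference. What stands is that the written definition of a primary outcome is wrong if the product is printed, whatever the code does.

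**The planned sensitivity analyses would reveal it.** Aims 1 and 6 also call for hit rate, false-alarm rate and overall accuracy. These could well expose a reversed k. The plan labels them exploratory, however, and they do not replace the primary score.

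**The simulated percentages rest on inputs that the plan does not give.** This is correct. No match/non-match split is described. Whether site varies within participants is also unsettled: Aim 1 in Section 11.1 calls it a within-participant factor, while Section 1.5 and the phase one introduction in Section 11.1 refer to parallel arms. The percentages are illustrations only.

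**Conclusion.** The concern holds for the text as supplied, subject to a check of the printed page. From the formula and the HR and FA definitions alone, the score rises with false alarms, equals N × FA when error rates are equal, and is zero for a perfect participant. An effect that lowers false alarms alone, or both error types equally, reverses sign within the titration window; the worked case is −0.100 against +0.147.

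Two stronger readings are not supported. The first is that every kind of error raises the score: misses alone lower it, and an effect confined to HR is attenuated, not reversed. The second is that the sample size is undermined: the figure of 48 reproduces from the stated effect size, which Section 11.2 describes as an effect on capacity, the evident intended endpoint.

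The difference form is inferred from a guessing model that the plan does not state. The size of any wrong-direction risk cannot be fixed from the documents.

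**What to change.** - Check the formula on the printed page of Section 11.1, Aim 1.
- If it shows a product, replace it with k = N × (HR − FA)/(1 − FA) and state that HR and FA are proportions. The text calls both a percent, but 1 − FA is meaningful only for proportions. Aim 6 inherits the correction.
- Test the scoring code on fixed cases: HR = 1 with FA = 0 must return N, and HR = FA (below 1) must return 0. Recompute any k already produced with the product.
- In the same correction, reconcile HR and FA with the task. Section 6.5.2 describes a colour-wheel response, and Aim 4 in Section 11.1 counts a response within 15 degrees as correct. Neither describes a match/non-match probe, so changing the sign does not by itself make the two rates obtainable. The plan should state how each is derived from the recorded responses.

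The formula change is one line plus a code check. Reconciling the definitions with the task takes more drafting and possibly rescoring. Correcting the formula needs no new participants or data.

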prefrontal cortex, and contrasted between a leftward and rightward retro-cue to derive the alpha frequency with peak amplitude in parietal cortex. These peak frequencies will be used for stimulation in the fourth and fifth session. In the third session, we will acquire a structural MRI and resting-state scan (10 minutes) for each participant. The resting-state functional MRI data will be analyzed using independent component analysis. This technique will identify regions in the anterior middle frontal gyrus and posterior intraparietal sulcus that are functionally connected within the frontal-parietal, "executive control," network. A previous meta-analysis of functional MRI studies found that the regions with peak retro-cue activity was at Montreal Neurological Institute coordinates (-40, 36, 28) for anterior middle frontal gyrus and (-38, -48, 44) for inferior intraparietal sulcus. Therefore, we will constrain our search lights to the anatomical landmarks and these coordinates. The center of mass in these regions will be used for targeting

CONFIDENTIAL

with TMS in the subsequent fourth and fifth sessions. In the fourth and fifth sessions, stimulation will be delivered at the timing relative to retro-cue, frequency, and spatial location based on our previous localizers. During stimulation, the location of the TMS coil needs to be aligned to the targeted brain region with neuro-navigation software that records the accuracy of each TMS pulse relative to the target (Localite, Sankt Augustin, Germany). On each trial, the stimulation type will be randomly selected, counter-balanced, and inter-mixed (see section 4.1 below). The effects of rhythmic TMS are not expected to last for more than a few cycles beyond stimulation itself (Thut et al. 2011; Hanslmayr et al. 2014; Albouy et al. 2017). Therefore, the experimental design randomly intermixes the stimulation type within every task block.

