Aim 2 (primary outcome): Stimulation is hypothesized to increase the targeted frequency of stimulation relative to arrhythmic stimulation. This aim will provide evidence of target engagement, i.e. that stimulation is effective at modulating the targeted rhythm. Using Morlet wavelet convolution, the amplitude of theta and alpha oscillations will be estimated during task performance. The average across trials for each conditions will be calculated and baseline corrected using decibels to the time before the encoding array (700 to 300 milliseconds). Then, the average amplitude within the individual theta (ITF  $+$ /- 1 Hz) and alpha frequency (IAF  $+$ /- 1 Hz) band will be calculated for the second half of the train of TMS pulses. Previous research has shown that amplitude increase from stimulation increases over the course of the TMS train. Frontal-theta and parietal-alpha amplitude values will be submitted to a two-way repeated-measures ANOVA with TMS frequency by TMS site. We hypothesize to find a significant interaction ( $p < 0.05$ ) between TMS site and TMS frequency such that theta amplitude in frontal cortex increases greater for TMS to frontal in theta frequency and alpha amplitude in parietal cortex increases greater for TMS to parietal cortex in alpha frequency. Post-hoc t-tests will be performed using Tukey's method to control for multiple comparisons. *Sensitivity analysis*: To understand the specificity of this effect, the time-course for the impact of stimulation of amplitude will be plotted as well as the topographic plot for our effects. Cluster analysis will be used to estimate the spread of our effect in time and space. These analyses provide evidence to the robustness of the

impact of stimulation on amplitude.

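### Aims 2 and 3 appear to correct each intermixed stimulation condition to its own pre-encoding baseline, which removes no bias and can cost precision in the primary EEG contrast

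*Combined protocol and SAP*

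**What the plan says.** Section 11.1, Aim 2 (primary outcome), describes Morlet amplitude, then: "The average across trials for each conditions will be calculated and baseline corrected using decibels to the time before the encoding array". The window is given as 700 to 300 ms. Band amplitude "will be calculated for the second half of the train of TMS pulses" and goes into a TMS site by TMS frequency ANOVA. Aim 3 (secondary) uses the same method on the other frequency band.

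Four other statements bear on this step:

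- Section 4: "On each trial, the stimulation type will be randomly selected, counter-balanced, and inter-mixed", and "Therefore, the experimental design randomly intermixes the stimulation type within every task block".
- Section 6.5.2: after one second of encoding and one second of delay comes the retro-cue. On TMS: "It is during this epoch, after the presentation of the retro-cue that TMS is delivered in sessions four and five".
- Section 11.1, Phase One: "All analyses will be performed on the difference from condition-matched arrhythmic TMS".
- Section 11.1, Phase One: "there are 75 trials for each condition per participant", a condition being a stimulation type with a cue direction.

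No section says whether the dB divisor belongs to the condition or is pooled over the session, and none justifies the choice.

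**The concern.** The baseline window closes 300 ms before the array. With 1 s of encoding and 1 s of delay, it closes at least 0.3 + 1 + 1 = 2.3 s before the train. Neither the stimulation type nor the cue direction of a trial can influence it, and trial types are assigned at random within the session. Rhythmic and arrhythmic trials therefore share the same expected baseline, and any observed difference between their baselines is chance.

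If one session baseline is the divisor, it cancels from the rhythmic-minus-arrhythmic dB contrast. If each condition has its own divisor, the chance difference stays in the contrast with a fixed weight of 1. That weight helps only if baseline and train-window amplitude move together strongly enough across a gap of more than two seconds. At stake is the precision of the target-engagement primary outcome, and of Aim 3.

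**Working it through.** **1. The plan's own figures.** Section 11.2 gives 44 participants for theta (effect 0.56), 21 for alpha (0.83) and 48 for working memory capacity (0.532), each at 95% power. An exact noncentral-t calculation for a paired t-test, two-sided alpha .05, returns 44, 21 and 48 (power .953, .951, .950). All three reproduce. At n = 48 the theta effect has power .967 and the alpha effect .9999.

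**2. The two contrasts.** Let p and b be the train-window and baseline values of a condition average in dB, with 1 = rhythmic and 0 = arrhythmic.

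- Common baseline: (p1 − b) − (p0 − b) = p1 − p0.
- Own baseline: (p1 − b1) − (p0 − b0) = (p1 − p0) − (b1 − b0), where b1 − b0 has expectation zero.

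**3. Variance ratios.** Let r be the variance of b1 − b0 divided by the measurement variance of p1 − p0, and rho their correlation. The documents give neither, so both are assumed over a range.

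- Own / common = 1 + r − 2·rho·√r. Break-even is at rho = √r / 2: .50 at r = 1, .43 at r = .75, .35 at r = .5.
- Own / covariate (slope estimated) = (1 + r − 2·rho·√r) / (1 − rho²) = 1 + (√r − rho)² / (1 − rho²). To first order this is never below 1.

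At r = 1 the second ratio simplifies to 2 / (1 + rho):

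| rho | Own / common | Own / covariate |
|---|---|---|
| 0 | 2.0 | 2.00 |
| .25 | 1.5 | 1.60 |
| .50 | 1.0 | 1.33 |
| .75 | 0.5 | 1.14 |

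**4. Plausible r.** Section 6.2 gives pulse spacings of about 200 ms (theta) and 100 ms (alpha). Five pulses span four intervals, so the second half of the train lasts about 400 ms for theta and 200 ms for alpha, against a 400 ms baseline. A simulation with these windows (1/f noise, 5-cycle wavelet, 75 trials per condition, added trial-to-trial amplitude shared by both windows) gave:

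| Band | rho | r | Own / common |
|---|---|---|---|
| Theta | −.03 | 1.09 | 2.16 |
| Theta | .30 | 0.99 | 1.39 |
| Theta | .57 | 1.10 | 0.90 |
| Theta | .71 | 1.11 | 0.62 |
| Alpha | −.04 | 0.62 | 1.69 |
| Alpha | .33 | 0.77 | 1.19 |
| Alpha | .55 | 0.70 | 0.77 |
| Alpha | .72 | 0.87 | 0.54 |

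**5. Effect on power.** Assume that 0.56 and 0.83 are the common-baseline effects, that all 48 participants contribute a paired contrast, and that a share q of the contrast variance is measurement noise. Total variance is multiplied by v = q·ratio + (1 − q), and the effect size becomes d / √v.

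| Ratio | q | v | Theta d | Theta power | Theta n for 95% | Alpha power |
|---|---|---|---|---|---|---|
| 1.0 | any | 1.00 | 0.560 | .967 | 44 | >.999 |
| 1.5 | .5 | 1.25 | 0.501 | .925 | 54 | .999 |
| 1.5 | 1 | 1.50 | 0.457 | .873 | 65 | .996 |
| 2.0 | 1 | 2.00 | 0.396 | .766 | 85 | .978 |
| 0.5 | 1 | 0.50 | 0.792 | >.99 | 23 | >.999 |

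The last row is the case in which own-condition correction helps.

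**The case against.** The strongest reply has four parts.

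- **The text does not name the divisor.** The phrase about each condition governs the averaging, and a session-pooled baseline also fits the sentence. This stands: own-condition correction is a reading. But a primary outcome should not leave the step open, and the remedy is the same on either reading.
- **The direction of the effect is not known.** A reader might infer that the plan necessarily adds noise to the contrast. The documents do not support that. Above rho = √r / 2 own-condition correction is the more precise of the two, and for alpha, with its shorter train window, break-even probably comes below .5. This stands against preferring a common baseline alone. It does not defend a fixed slope of 1, because an estimated slope is at least as good to first order at every r and rho.
- **Both conventions are unbiased.** This also stands. A reader might infer a biased contrast or an inflated false-positive rate, but random intermixing and equal trial counts exclude that. The issue is precision only.
- **A covariate seems to need a trial-level model**, whereas the plan averages before converting to dB. It does not need one. The participant's own baseline difference, already available from the condition averages, is enough.

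**Conclusion.** The point holds as a matter of precision and specification. As most naturally read, Aim 2 and by inheritance Aim 3 subtract a chance baseline difference at a fixed slope of 1, with no bias to remove. Against a common baseline, the measurement-noise variance ratio runs from about 2 at zero correlation, through 1 near a correlation of .5 (equal variances assumed), to below 1 above that.

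For theta, where the plan needs 44 of its 48 participants, a ratio of 1.5 would lower power from .967 to .925 or .873, depending on the noise share. Alpha has ample margin. These figures rest on an assumed ratio and noise share, and on treating 0.56 as a common-baseline effect. The cited theta study may already include a similar baseline step. They also assume a paired contrast in all 48, and the current text is not settled on whether site is within or between participants. It would therefore be wrong to conclude that the study is underpowered for Aim 2: the .766 figure is a worst case, not an estimate.

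**What to change.** In section 11.1, Aim 2, and by reference Aim 3:

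1. State that the dB baseline is one value per participant-session and band, averaged over all trials whatever the stimulation type and cue.
2. Adjust the rhythmic-minus-arrhythmic contrast for the matching baseline difference, with an estimated slope. For the site by frequency interaction, the covariate is the same combination of baseline differences as the outcome contrast. Participant-level is enough; trial-level is optional.
3. In a paired analysis, enter the covariate uncentred, so that the effect is read at a baseline difference of zero, its expected value under randomisation. Centring at the sample mean would leave the estimate unadjusted while its standard error shrank by √(1 − rho²).
4. Report the condition-specific baseline version as a sensitivity analysis.

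The cost is one degree of freedom, two or three sentences and a small script change. No new data are needed. The choice should be fixed before the EEG contrasts are examined.
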